5.1.9 Premature discontinuation of ponesimod

The decision to prematurely discontinue study treatment may be made by the subject, the investigator or Actelion.

A subject has the right to prematurely discontinue study treatment at any time by withdrawal from treatment only or by withdrawal from treatment and any further participation in the study.

The investigator should discontinue study treatment for a given subject if, on balance, he/she believes that continued administration would be contrary to the best interests of the subject.

Premature discontinuation of study treatment may also result from a decision by Actelion, e.g., in case of premature termination or suspension of the study [see Section 9.3].

The main reason and whether discontinuation of study treatment is the decision of the subject, the investigator or Actelion must be documented in the eCRF.

A subject who prematurely discontinues study treatment is NOT considered as withdrawn from the study and will be followed up until the end of the safety follow-up period (30 days after study drug discontinuation), provided that the subject's consent for this limited participation in the study has not been withdrawn.

A subject who prematurely discontinues study treatment and withdraws consent to participate in any further study assessments is considered withdrawn from the study. Subjects who die or are lost to follow-up are also considered as withdrawn from the study. Withdrawal from the study and follow-up medical care of subjects withdrawn from the study is described in Sections 9.2 and 9.4, respectively.

5.1.10 Specific dose-reduction, interruption, or premature discontinuation criteria

Ponesimod should be prematurely discontinued before initiating rescue IS therapy or other forbidden medications during the Core Treatment Period. Ponesimod should also be prematurely discontinued before initiating forbidden medications during the Extension Treatment Period. See Section 5.3.5.

Ponesimod-specific dose reduction, interruption, or premature discontinuation criteria are presented for a variety of conditions and scenarios grouped according to the following organ systems. These criteria apply during both the Core and Extension Treatment Periods:

- (1) Cardiovascular
- (2) Hematologic
- (3) Hepatobiliary
- (4) Immune/infection

- (5) Ocular
- (6) Reproductive/pregnancy
- (7) Respiratory

5.1.10.1 Cardiovascular

Ponesimod must be discontinued if any of the following are true at any time:

- 1) The following are observed and also documented by ECG at any time during the study:
 - a) HR < 40 bpm, or
 - b) HR < 60 bpm is sustained for at least 1 hour and is associated with symptoms of bradycardia (e.g., syncope, dizziness, or vertigo), or
 - c) QTcF > 500 ms is observed at any time throughout the study.
- 2) The subject does not meet the criteria for discharge from hospital on Day 1, EX-1 or on the first day of re-initiation of ponesimod following drug interruptions after 12 h post-dose monitoring.
- 3) The subject needs to receive systemic chronic treatment with β -blockers, diltiazem, verapamil, digoxin, digitoxin, or any other anti-arrhythmic or HR-lowering therapy (non-exhaustive list of drugs provided in Appendix 4).
- 4) Subject experiences *de novo* or worsening of pre-existing hypertension that cannot be adequately controlled by medications.

Continuous ECG monitoring is recommended for subjects who meet ponesimod discontinuation criteria related to bradycardia or other arrhythmias. Subjects who are prematurely discontinued may be discharged from the monitored setting only after the following criteria are met:

Mandatory discharge from the clinic/hospital criteria for subjects discontinued due to bradycardia or other arrhythmias:

- Vital signs return to near baseline values.
- No persisting ECG abnormality (e.g., AV block second degree or higher).
- No ongoing AE requiring continued hospitalization.
- Absence of any other medical indication to remain in the monitoring setting.

Confidential

At Visits 3, 4, 5, 6 and 7 (Weeks 4, 8, 12, 16 and 20) in the Core Treatment Period and Visits EX-2, EX-3, EX-4, EX-5, EX-6, EX-7, EX-8, EX-9, EX-10, EX-11, and EX-12 (Extension Weeks 4, 8, 12, 16, 20, 24, 36, 48, 60, 72, and 84) in the Extension Treatment Period, 12-lead ECG measurements are collected pre-dose. In the event of a grade 2 QTc elevation, a repeat 12-lead ECG must be collected 3 hours post-dose. If QTcF > 500 ms, the subject is prematurely discontinued from the study. In addition, a PK sample must be collected within 20 minutes after the 3 hour post-dose ECG.

Any clinically relevant finding found after ponesimod initiation and during the follow-up period and meeting the definition of an AE will be recorded accordingly in the eCRF.

5.1.10.2 Hematologic

Ponesimod must be prematurely discontinued for any of the following laboratory findings at any time:

- Confirmed neutrophil count $< 0.5 \times 10^9/L$ ($< 500 \text{ cells/mm}^3$).
- Confirmed absolute lymphocyte count $< 0.1 \times 10^9/L$ ($< 100 \text{ cells/mm}^3$), and subject is receiving ponesimod 5 mg daily or less.

Ponesimod must be prematurely discontinued or, alternatively, the dosage must be reduced (dose reduction) for the following laboratory finding at any time:

- Confirmed absolute lymphocyte count $< 0.1 \times 10^9/L$ ($< 100 \text{ cells/mm}^3$), and subject is receiving ponesimod 10 mg or 20 mg.

Confirmation will be done as follows:

Whenever a neutrophil count $< 0.5 \times 10^9/L$ ($< 500 \text{ cells/mm}^3$) or an absolute lymphocyte count $< 0.1 \times 10^9/L$ ($< 100 \text{ cells/mm}^3$) is recorded by the central laboratory, an alert will be sent to the principal investigator and the sponsor. The site will immediately contact the subject and ask her/him to return to the site within 48 hours at the latest to repeat the test at trough level (pre-dose) by the central laboratory (unless the clinical situation mandates immediate local testing). If the repeat test confirms a neutrophil count $< 0.5 \times 10^9/L$ ($< 500 \text{ cells/mm}^3$) or an absolute lymphocyte count $< 0.1 \times 10^9/L$ ($< 100 \text{ cells/mm}^3$), then ponesimod must be discontinued or dose reduced according to the criteria above.

Monitoring for prematurely discontinued subjects

Neutrophil or lymphocyte counts must be monitored at least once a week by the local laboratory until the neutrophil count has returned to $\geq 80\%$ of the baseline value or the absolute lymphocyte count has returned to $\geq 0.5 \times 10^9/L$ ($\geq 500 \text{ cells/mm}^3$) or $\geq 80\%$ of the baseline value. Any clinically relevant finding found after ponesimod initiation and

Confidential

during the follow-up period and meeting the definition of an AE will be recorded accordingly in the eCRF.

Dose reduction and monitoring

For those subjects qualifying for dose reduction, the previously tolerated dose is immediately instituted without dose interruption. For subjects currently on ponesimod 10 mg, the 5 mg dose is restarted. For subjects on 20 mg, the 10 mg dose is restarted. Subjects remain on the lower dose for the remainder of the study, with no further dose-escalation. Lymphocyte counts are repeated at the next scheduled study visit after dose-reduction (or earlier per investigator judgment), and **if the absolute lymphocyte count remains $< 0.1 \times 10^9/L$ ($< 100 \text{ cells/mm}^3$) ponesimod is discontinued.** Hematologic monitoring for prematurely discontinued subjects is continued as per above.

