3.2.4 Extension Treatment Period

Subjects who completed the 24 weeks of study treatment (i.e., who were not prematurely discontinued from ponesimod) and whose chronic GVHD progressed after EOT1 may be restarted on study drug at least 7 days after EOT1 and no later than 90 days after EOT1.

The Extension Treatment Period starts the day ponesimod is started, on visit EX-1 (Visit 11) and can continue for up to 96 weeks. Visits during the Extension Treatment Period will consist of visit EX-1 and visits at EX-Weeks 4, 8, 12, 16, 20, 24, 36, 48, 60, 72, 84, and 96.

The End-of-Treatment 2 (EOT2) visit will take place at EX-Week 96, EX-13 (Visit 23) or earlier in case of premature discontinuation of study drug. In all cases, the EOT2 visit should take place not later than 7 days after the last dose of study drug.

[figure not shown]
Subjects completing the EOT2 will be subsequently treated according to local standard of care at the investigator's discretion.

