For these local laboratories, the investigator/delegate will provide Actelion with the name, professional degree and curriculum vitae of the laboratory director, a copy of the laboratory's certification, and the normal ranges for each laboratory test that is evaluated in the study. These laboratory references must be updated whenever necessary.

In case a central laboratory sample is lost, has deteriorated or cannot be analyzed for whatever reason, the investigator will collect an additional sample as soon as possible for repeat analysis if still clinically relevant.

The central laboratory will provide all laboratory results by fax or normal mail to the site.

All laboratory reports must be signed and dated by the principal investigator or delegate within 5 calendar days of receipt and filed with the source documentation. The investigator/delegate must indicate on the laboratory report whether abnormal values are considered clinically relevant or not. Clinically relevant laboratory findings meeting the definition of an AE [see Section 10.1.1] must be reported as an AE or SAE as appropriate [see Section 10], and must be followed until the value returns to within the normal range or is stable, or until the change is no longer clinically relevant. Further laboratory analyses should be performed as indicated and according to the judgment of the investigator.

Details about the collection, sampling, storage, shipment procedures, and reporting of results and abnormal findings can be found in the laboratory manual.

7.3.11.2 *Laboratory tests*

Blood samples will be drawn before the morning administration of study medication, at visits indicated in Table 1. Urinalysis will be assessed using dipsticks at visits indicated in Table 1.

Hematology

- Red blood cell count
- Total and differential WBC counts (basophils, eosinophils, lymphocytes, monocytes, neutrophils, band forms)
- Platelet count
- Hb
- Hematocrit

Clinical chemistry

- Glucose
- ALT, AST, alkaline phosphatase, TBL, lactate dehydrogenase

- Creatinine
- Calculated creatinine clearance (Cockroft-Gault)
- INR
- Urea
- Uric acid
- Total cholesterol
- Triglycerides
- Sodium, potassium, chloride, calcium
- Total protein, albumin
- C-reactive protein

Virus serology

- Hepatitis B surface antigen, Hepatitis C antibodies, HIV1 and HIV2 antibodies at Visit 1 (screening)

Additional analyses in the event of infections

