8.4.2 Visits 12, 13, 15, and 16 (EX-2, EX-3, EX-5, and EX-6), Extension Weeks 4, 8, 16, and 20

The visit window for these visits is +/- 7 days.

- Recording of changes in concomitant medications
- Assessing and recording of MOC (for WOCBP only)
- SBP/DBP (pre-dose)
- 12-lead ECG (pre-dose)
- Hematology, blood chemistry
- Urinalysis
- Urine pregnancy test for WOCBP (if applicable)
- Recording of AEs and SAEs
- Study medication accountability and compliance review
- IRT call and study drug dispensing
- Remind WOCBP to use the MOC defined for this study. The reminders must be documented in the hospital chart.
- Schedule an appointment for next visit and instruct subject to:

- bring back any bottles or blister wallets
- not take study treatment on the day of study visit prior to coming to the site

8.4.3 Visits 14, 17, 18, 19, 20, 21, and 22 (EX-4, EX-7, EX-8, EX-9, EX-10, EX-11, and EX-12), Extension Weeks 12, 24, 36, 48, 60, 72, and 84

The visit window for these visits is +/- 7 days.

- Administer Chronic GVHD Activity Assessment – Patient self-report [Appendix 7 – Form B]
- Administer LSS (subject completes the questionnaire after patient self-report but prior to any clinical assessments or interaction with health care providers, preferably while waiting for their appointment)
- Chronic GVHD Activity Assessments - physician assessed [Appendix 7 – Form A]
- Recording of changes in concomitant medications
- SBP/DBP (pre-dose)
- 12-lead ECG (pre-dose)
- Assessing and recording of MOC (for WOCBP only)
- Body weight
- Physical examination
- Spirometry (pre-dose; under the responsibility of the pulmonologist)
- DLco (pre-dose; under the responsibility of the pulmonologist)
- OCT, visit EX-4 only (under the responsibility of the ophthalmologist)
- Ophthalmological examination, visit EX-4 only (under the responsibility of the ophthalmologist)
- Hematology, blood chemistry (pre-dose)
- PD sampling (pre-dose)
- Urinalysis
- Urine pregnancy test for WOCBP (if applicable)
- Recording of AEs and SAEs
- Study medication accountability and compliance review
- IRT call and study drug dispensing
- Remind WOCBP to use the MOC defined for this study. The reminders must be documented in the hospital chart
- Schedule an appointment for next visit and instruct subject to:
 - bring back any bottles or blister wallets
 - not take study treatment on the day of study visit prior to coming to the site

Confidential

8.4.4 Visit 23 (EX-13, EOT2) Extension Week 96

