8.5.2 Unscheduled visits for reasons other than re-initiation of study drug

Unscheduled visits may be performed at any time during the study for reasons other than re-initiation of study drug. Depending on the reason for the unscheduled visit (e.g., loss of efficacy, AE, etc.), appropriate assessments may be performed based on the judgment of the investigator and must be recorded in the eCRF. After an unscheduled visit, the regular scheduled study visits must continue according to the planned visit and assessment schedule.

Unscheduled visit assessments may include:

- Assessment of concomitant medications
- Assessment of MOC (for WOCBP only)
- PFTs
- SBP/DBP (pre-dose)
- 12-lead ECGs (e.g., in case of need of concomitant treatment with a QT prolonging drug with known risk of Torsades de Pointes [see Appendix 3], pre-dose).
- Ophthalmological examination
- OCT (e.g., presence of visual symptoms suggestive of macular edema)
- Spirometry (under the responsibility of the pulmonologist)

Confidential

- DLCO (under the responsibility of the pulmonologist)
- Physical examination
- Measurement of body weight
- Complete laboratory tests including: hematology, blood chemistry, urinalysis, or serum pregnancy test (for WOCBP only)
- Assessment of AEs and SAEs
- Return of study drug blisters and unused medication and dispensing of new blisters, if appropriate.

Additional unscheduled spirometry will have to be conducted in the event of respiratory symptoms (e.g., dyspnea) during the course of the study. Administration of inhaled short-acting β_2 agonists (e.g., albuterol/salbutamol) for symptom relief may be performed at the discretion of the investigator. Administration of short-acting β_2 agonists will be collected in the eCRF.

If any of the laboratory parameters listed in Section 7.3.11.2 need to be analyzed, this must be done at the central laboratory, except in case of emergency; if it has been done at a local laboratory, results must be recorded in the eCRF [see Section 7.3.11].

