10 SAFETY DEFINITIONS AND REPORTING REQUIREMENTS

10.1 Adverse events

10.1.1 Definitions of adverse events

An AE is any adverse change, i.e., any unfavorable and unintended sign, including an abnormal laboratory finding, symptom or disease that occurs in a subject during the course of the study (beginning with signing of the ICF), whether or not considered by the investigator as related to study treatment.

A treatment-emergent AE is any AE temporally associated with the use of study treatment (from study treatment initiation until 30 days² after study treatment discontinuation) whether or not considered by the investigator as related to study treatment.

AEs include:

- Exacerbation of a pre-existing disease.
- Increase in frequency or intensity of a pre-existing episodic disease or medical condition.
- Disease or medical condition detected or diagnosed during the course of the study even though it may have been present prior to the start of the study.
- Continuous persistent disease or symptoms present at study start that worsen following the start of the study.
- Abnormal assessments, e.g., change on physical examination or ECG findings if they represent a clinically significant finding that was not present at study start or worsened during the course of the study.
- Laboratory test abnormalities if they represent a clinically significant finding, symptomatic or not, which was not present at study start or worsened during the

² Should cover at least 5 elimination half-lives, if more than 30 days.

Confidential

course of the study or led to dose reduction, interruption or premature discontinuation of study treatment.

Overdose, misuse and abuse of the study treatment should be reported as an AE and, in addition, study treatment errors must be documented in the study drug log of the eCRF.

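### After a dose reduction for a confirmed lymphocyte count below 0.1 × 10⁹/L, the deciding repeat count is tied only to the next scheduled visit, which in the late Extension is about 12 weeks away

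*Combined protocol and SAP*

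**What the plan says.** Section 5.1.10.2 (Hematologic) gives two options when a count below 0.1 × 10⁹/L is confirmed on 10 or 20 mg: stop ponesimod, or step down at once to the previous dose (20 to 10 mg, 10 to 5 mg). After a step down, "Lymphocyte counts are repeated at the next scheduled study visit after dose-reduction (or earlier per investigator judgment"), and a count still below 0.1 means the drug is discontinued. The parent section, 5.1.10, says of these rules: "These criteria apply during both the Core and Extension Treatment Periods".

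Core visits are every 4 weeks to Week 24 (Section 3.2.2). The Extension (Section 3.2.4) has "visits at EX-Weeks 4, 8, 12, 16, 20, 24, 36, 48, 60, 72, 84, and 96", so the spacing changes from 4 to 12 weeks at EX-Week 24. For the on-treatment Extension visits, Sections 8.4.2 and 8.4.3 state: "The visit window for these visits is +/- 7 days". Section 8.4.4 gives EX-Week 96 the same window.

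For subjects who stop the drug because of the count, Section 5.1.10.2 is stricter: "Neutrophil or lymphocyte counts must be monitored at least once a week by the local laboratory", until recovery.

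**The concern.** The repeat count decides whether a subject who is still taking the drug must stop. Its only fixed time is borrowed from the visit schedule, and that schedule becomes three times sparser after EX-Week 24.

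Two comparisons make this look unintended. A subject who stops the drug for the same count is checked weekly, while the subject who stays exposed has no stated limit. And in Section 5.1.10.3, a subject restarted at a lower dose after a liver-test interruption has liver tests repeated at 5–7 and 10–12 days and then monthly, in the Extension as well. The liver case follows an interruption rather than an immediate step down, so the parallel is not exact, but it shows that the protocol sets fixed times elsewhere.

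At stake is time on drug with a count that the protocol itself treats as a reason to stop, in transplant recipients already at raised risk of infection. The Amendment 3 rationale supports the lower 0.1 threshold partly because counts recover within days once treatment is interrupted. That protection works only if someone learns in time that the drug has to stop.

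**Working it through.** **Check of the schedule against the plan's own figure.** Table 8 (Section 7.7) lists 14 hematology tests for the Extension and Follow-up Period 2. From the visit list: EX-1, plus 12 visits (EX-2 to EX-13), plus FU3 = 14; 14 × 3 mL = 42 mL, as printed. With chemistry, 42 + 14 × 7.5 = 147 mL, also as printed. So no hematology draw is scheduled between the quarterly visits.

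**Gap between consecutive visits.** Nominal gap = weeks × 7. Maximum = nominal gap + window of the earlier visit + window of the later visit. Windows are set from a fixed reference day, so they do not accumulate.

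| Interval | Nominal (days) | Maximum (days) |
|---|---|---|
| Core, Weeks 4 to 8 (± 3 and ± 3) | 28 | 28 + 3 + 3 = 34 |
| Core, Weeks 8 to 12 (± 3 and ± 7) | 28 | 28 + 3 + 7 = 38 |
| Core, Weeks 12 to 24 (± 7 each) | 28 | 28 + 7 + 7 = 42 |
| Extension, EX-Weeks 4 to 24 | 28 | 28 + 7 + 7 = 42 |
| Extension, EX-Weeks 24 to 96 | 12 × 7 = 84 | 84 + 7 + 7 = 98 |

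The dose is cut only after confirmation, for which the subject must return within 48 hours. Taking off the full 2 days leaves 82 days nominal and 96 days at most from the cut to the next scheduled count.

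**How much of the Extension is affected.** (96 − 24)/96 = 72/96 = 75% of its weeks. Of the 11 on-treatment visits before EX-Week 96, six (EX-Weeks 24, 36, 48, 60, 72 and 84) are followed by a 12-week gap.

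**Time gained by a 4-week limit.** 84 − 28 = 56 days (8 weeks); 98 − 28 = 70 days (10 weeks). After the 2-day confirmation: 82 − 28 = 54 and 96 − 28 = 68 days.

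**Could a count stay below 0.1 after one step down?** This is an illustration only, and it assumes that mean effects apply proportionally to an individual. The mean decreases of 30%, 50% and 65% at 5, 10 and 20 mg (Amendment 3 rationale) give factors of 0.50/0.35 = 1.43 (20 to 10 mg) and 0.70/0.50 = 1.40 (10 to 5 mg). The planning means in Section 11.4.2 give 0.60/0.40 = 1.50 and 0.85/0.60 = 1.42. A triggering count would then need to be at least about 0.1/1.50 = 0.067 to 0.1/1.40 = 0.071 to get back to 0.1. Recovery is thus plausible for counts just under 0.1 and not assured for lower ones. These are population means applied to extreme individuals, so they do not identify who would be affected.

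**The case against.** **The safeguards are real.** The rule itself allows earlier testing. A central-laboratory count below 0.1 alerts both the investigator and the sponsor (5.1.10.2). The sponsor's team reviews laboratory values continuously (10.4), and the Study Monitoring Committee reviews each subject's toxicity (3.5.1). A clinically significant abnormality that, in the words of 10.1.1, "course of the study or led to dose reduction, interruption or premature discontinuation of study treatment" is an adverse event, and under 7.3.11.1 relevant laboratory findings of this kind "must be followed until the value returns to within the normal range or is stable, or until the change is no longer clinically relevant". At unscheduled visits "appropriate assessments may be performed based on the judgment of the investigator" (8.5.2). A careful investigator would very likely test early, and a reader should not infer that these subjects go unmonitored. What remains is that none of these provisions sets a time. An alert follows a count but does not cause one to be drawn, and a site that waits for the quarterly visit has complied with 5.1.10.2.

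**The event is probably rare.** Core entry requires a screening count of at least 0.5. At the mean 20 mg effect this becomes 0.5 × 0.35 = 0.175. Falling below 0.1 from 0.5 needs a reduction of more than 1 − 0.1/0.5 = 80%, while Section 1.3.2.2 puts the maximum at about 65–80%, reached at doses above any used here. Subjects also restart a dose they tolerated (5.1.1), on which the effect is described as stable. This stands, but it does not exclude the event. The 65% is a mean, the Extension has no lymphocyte entry limit, and systemic immunosuppressant dosing is unrestricted there. The protocol's remark that such treatments can lower the count further was written about patients as early as 3–4 months after transplant, and agents not prescribed per protocol remain forbidden, so this mechanism should not be pressed hard.

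**A 12-week delay might be inferred.** That overstates it. Twelve weeks is the whole wait; the avoidable part, against a 4-week limit, is about 8 weeks.

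**Conclusion.** The point holds for the late Extension and is a cheap improvement, not an error in the analysis. From EX-Week 24 to EX-Week 96, a subject kept on a reduced dose after a confirmed count below 0.1 can, in full compliance with 5.1.10.2, wait 84 days (up to 98) between the triggering visit and the next scheduled count, slightly less from the dose cut itself. A stop that the protocol requires could be found about 8 weeks (up to 10) later than under a 4-week limit.

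This assumes that the low count is found at a scheduled visit and that nobody uses the discretion to test sooner; either would shorten the wait. The documents give no frequency for the event, and none is claimed. In the Core and up to EX-Week 24 the nominal wait is already 4 weeks. The primary pharmacodynamic analysis uses Core Weeks 4, 8 and 12, so it and the sample size are untouched.

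**What to change.** In Section 5.1.10.2, replace the sentence on the repeat count with wording such as: 'The lymphocyte count is repeated no later than 4 weeks after the dose reduction, sooner if the investigator sees reason. A scheduled visit is used if one falls in that time, otherwise an unscheduled hematology draw. If the count is still < 0.1 × 10⁹/L, ponesimod is stopped.' The threshold does not change.

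Advising sites to draw at about 2 weeks or later is reasonable, so that the count reflects the lower dose, but the documents do not require it. The 2 to 3 weeks in Section 3.3 describe onset after starting the drug, whereas recovery after stopping takes about a week (1.3.2.2) and steady state 4–5 days (1.3.2.1). The change limits only the first repeat; a subject who recovers to just above 0.1 returns to the quarterly schedule unless the investigator decides otherwise.

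Cost per affected subject: one 3 mL draw (3/147 = 2.0% of the planned Extension volume; Table 8 already foresees extra samples for counts this low) and possibly one unscheduled visit, which 8.5.2 permits. Before EX-Week 24 an extra draw is needed only when visit windows or an unscheduled trigger push the next visit beyond 4 weeks after the cut. The one-sentence change still needs a written amendment submitted to the ethics committee and the authorities (13.6), so it is best combined with the next one.
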